### 4.8 SESSION AND RESPONSE WINDOWS

#### 4.8.1 V2 Session Window

Participants may attend V2 up to 30 days post Screening Session (V1).

#### 4.8.2 All other visit Windows

Participants may attend sessions up to four-calendar day's pre or post the scheduled visit.

#### 4.8.3 SMS Response Window

The SMS response window will be open until the next SMS message is sent.

## 5 HALO-G6 ELECTRONIC NICOTINE DELIVERY SYSTEM

---

### 5.1 DESCRIPTION OF HALO G6

The Halo G6 is a breath-actuated, rechargeable e-cigarette that comes with prefilled e-liquid cartomizers. This e-cigarette was chosen over other tank-based or pod-based e-cigarette models because of its similarity in shape and size to a cigarette. Because one of the goals is to provide habit substitution for smoking that zonisamide/bupropion cannot provide, this “cigalike” design is considered advantageous.

### 5.2 DESCRIPTION OF E-LIQUID

Each G6 prefilled cartomizer contains a 50/50 blend nicotine salt with 35 mg nicotine strength. The 3.5% nicotine concentration was chosen over higher (e.g. 5%) concentrations to reduce the likelihood of nausea. The cartomizers come in packs of five. All Halo brand e-liquids undergo independent testing and they are manufactured by Nicopure labs.

This study will use “Tribeca” (tobacco) and “Menthol” flavored cartomizers, with participants matched to their preferred cigarette flavor. At Visit 2, participants will be allowed to use the device *ad libitum* for a maximum of 10 minutes. Research staff will inquire whether the participants are willing and able to use the Halo G6 during the study, to determine eligibility.

### 5.3 PRODUCT USE TIMEFRAME

The maximum amount of time the G6 will be in use will be for 13 weeks, plus up to an additional four days (to allow for the scheduling window). Participants will be instructed on how to use the e-cigarette prior to dispensing.

### 5.4 ACCOUNTABILITY AND COMPLIANCE

The G6 will be dispensed by the Investigator or designated study staff, as per study design. Participants will be dispensed cartomizers initially at 125% based on their daily smoking habits as reported at baseline (one per pack of cigarettes smoked per day). Participants may come into the office between visits to get additional supplies if needed. Each dispensation and collection of the product will be recorded.

#### 5.4.1 Storage and Accountability

All products will be stored in a locked, limited-access area at the study site and kept at an ambient controlled room temperature, with excursions documented by RRC standard operating procedures. Halo products should not be exposed to extreme heat or cold.

#### 5.4.2 Compliance

Compliance will be ensured by strict distribution of the product and collection of devices (used and unused) which will be documented in appropriate logs.

## 6 ZONISAMIDE

---

### 6.1 DESCRIPTION OF ZONISAMIDE

Zonisamide is currently marketed as an antiepileptic medication for treatment of partial seizures. While the main mechanism of action is believed to be related to its sodium and calcium channel blockade, the medication is suspected of exerting dose-dependent biphasic dopaminergic and serotonergic activity. As noted in Section 1.1, this medication has been shown to reduce ad libitum smoking and relieve craving from cigarettes. Zonisamide also has been shown to decrease anger, restlessness and impatience during smoking abstinence. The combination of bupropion and zonisamide has been studied as a treatment for weight loss in obese adults.

### 6.2 DOSAGE

Dosing of zonisamide will remain unchanged for the duration of the 12-week dosing period unless changed per guidance below (section 6.3). Participants will take 100 mg (two 50 mg capsules) orally once a day.

### 6.3 DOSE ADJUSTMENT PROCEDURES

Zonisamide will be dispensed in the form of a 50 mg capsules. Adjustments may be made to the timing of the dose (AM or PM) or the amount (1 or 2 capsules) depending on the somnolence/activation experienced by each individual participant. Initially, both bupropion and zonisamide will be taken in the morning. Should participants experience significant drowsiness, the medical providers (MD/PA) may change the dosing to nighttime (2 hours prior to bedtime) or decrease the dose to one 50 mg capsule per day. All dosing adjustments will be approved by the Medical Director for this study.

### 6.4 ACCOUNTABILITY AND COMPLIANCE

#### 6.4.1 Dispensing Product

Zonisamide will be dispensed by the Investigator or designated study staff utilizing blister-pack technology to enhance compliance and accountability. Each dispense and collection of the product will be recorded during each laboratory visit (Visit 3 through Visit 6). All study-related drug will be collected at the End-Of-Study (Visit 7 or early termination).

Prior to dispensing, the site will ensure that the product packaging is labelled with the protocol number and unique participant identifiers, date it was dispensed, and the statements "For investigational use only" and "Keep out of reach of children".

#### 6.4.2 Storage and Accountability

Zonisamide will be stored in a climate-controlled secured-storage site with access limited to the authorized personnel only. Full accountability of the distributed products will be ensured by designated staff.

#### 6.4.3 Compliance

Compliance will be ensured by strict distribution of the product, daily SMS messages, and collection of unused products at each study session. This information will be documented in appropriate logs.

## 7 BUPROPION

---

### 7.1 DESCRIPTION OF BUPROPION

Bupropion inhibits reuptake of both noradrenaline and dopamine. This medication has been approved as an antidepressant for over 20 years. The Food and Drug Administration approved the use of bupropion for smoking cessation in 1997. It is only one of two medications currently approved by the FDA for this purpose. The combination of bupropion and zonisamide has been studied as a treatment for weight loss in obese adults. The usual dose for bupropion for smoking cessation is 150 mg once a day for 3 days, followed by 300 mg once a day for 7 to 12 weeks. The maximum prescribed dose for bupropion is 450 mg a day, which is the maximum dose for treating major depressive disorder and attention deficit hyperactivity disorder for adults.

### 7.2 DOSAGE

- 150 mg tablet orally once a day for 3 days.
- Two 150 mg tablets (300 mg) orally once a day for the remainder of study participation.

### 7.3 DOSE ADJUSTMENT PROCEDURES

Bupropion will be dispensed in the form of a 150 mg extended release tablet, initially one tablet daily for 3 days, followed by 2 tablets daily until End of Study. Extended release tablets have a half-life that supports once daily dosing. Combining this medication with zonisamide will decrease the risk for side-effects, allowing for daily dosing, which will likely improve compliance. Adjustments will be made depending on the side-effects experienced by each individual participant. Initially, both bupropion and zonisamide will be taken in the morning. Should participants experience significant activation during the day, the medical providers (MD/PA) may either adjust the dose down to 150 mg daily or split the dose (150 mg taken twice daily which is normal dosing for smoking cessation). All dosing adjustments will be approved by the Medical Director for this study.

### 7.4 ACCOUNTABILITY AND COMPLIANCE

#### 7.4.1 Dispensing Product

Bupropion will be dispensed by the Investigator or designated study staff utilizing blister-pack technology to enhance compliance and accountability. Each dispense and collection of the product will be recorded during each laboratory visit (Visit 3 through Visit 6). All study-related drugs will be collected at the End-Of-Study (Visit 7 or early termination).

Prior to dispensing, the site will ensure that the product packaging is labelled with the protocol number and unique participant identifiers, date it was dispensed, and the statements "For investigational use only" and "Keep out of reach of children".

#### 7.4.2 Storage and Accountability

Bupropion will be stored in ambient climate-controlled secured-storage site with access limited to the authorized personnel only. Full accountability of the distributed products will be ensured by designated staff.

### 7.4.3 Compliance

Compliance will be ensured by strict distribution of the product, daily SMS messages, and collection of unused products at each study session. This information will be documented in appropriate logs.

## 8 STUDY PROCEDURES AND ACTIVITIES

---

Personnel performing study assessments must have appropriate and documented training. An overview of all study assessments is shown in the schedule of events (Section 7.5). Study personnel will adhere to standard operating procedures (SOPs) for all activities. Appropriate medical advice will be provided by qualified staff (licensed providers) to the participant in case of any medical findings requiring health care.

### 8.1 INFORMED CONSENT AND GUIDANCE

Prior to any study assessments being performed, the participant will be asked to provide their written consent to participate in the study on an informed consent form (ICF). All assessments must start after the time of ICF signature by the participant for study participation.

Designated staff, under the supervision of the Principal Investigator, will obtain informed consent from each participant. The person obtaining consent provides the participants with a printed document that explains the procedures and risks. Designated staff will answer any questions. A signed copy of the informed consent form will be given to each participant. Participants are informed that they may withdraw from participation in the study at any time without penalty.

Because of the nature of this study and the number of questionnaires that participants are expected to complete, we do not recruit potential participants who do not read, are blind, or who do not understand English. We are not equipped to validate alternate versions of our questionnaires, most of which are not published. Questionnaires cannot be administered orally by a translator or by technicians to illiterate or blind participants because the data obtained would not be comparable to self-administered questionnaires.

### 8.2 SAFETY LABORATORY AND OTHER ASSESSMENTS

An overview of all assessments is provided in the schedule of events.

Non-fasting blood samples and urine samples will be collected by qualified and trained site personnel. Participants will be in a seated or in a supine position during blood collection.

The maximal total volume of blood drawn for each participant will be around 30 mL for clinical chemistry, hematology, and serum pregnancy (for females).

Samples for clinical chemistry, hematology, and serum pregnancy test will be sent to LabCorp for analysis. Urinalysis will also be performed by LabCorp.

The results of the clinical chemistry, hematology and urine analysis safety panel will not routinely be given to participants to send or be sent to their physician to include in their medical record. However, if the participant's laboratory results are clinically relevant (including positive pregnancy tests), the research medical staff will send the participant a copy of the laboratory results. Participants who are accepted into the study but need medical

follow-up due to minor abnormalities in laboratory results (at any session) will also receive a copy of the laboratory results.

### 8.2.1 Safety Laboratory

Safety laboratory includes clinical chemistry, hematology, and urinalysis and will be assessed at Visit 1.

#### 8.2.1.1 Clinical Chemistry

Clinical Chemistry	
Sodium	Chloride
Potassium	Carbon dioxide
Blood urea nitrogen (BUN)	Creatinine
Glucose	Calcium
Total protein	Albumin
Bilirubin	Alkaline phosphatase (AP)
Aspartate aminotransferase (AST)	Alanine aminotransferase (ALT)

#### 8.2.1.2 Hematology

Hematology	
Red blood cell (RBC) count	WBC count
Hemoglobin	Differential white blood cell (WBC) count
Hematocrit	Platelet count
Mean corpuscular volume (MCV)	Mean corpuscular hemoglobin concentration (MCHC)
Mean corpuscular hemoglobin (MCH)	

### 8.2.2 Urine Samples

Urine samples will be collected for the urine drug screen (at screening session), urine pregnancy test (at all sessions except screening), and safety urinalysis (at screening session). The urine drug screen and pregnancy tests will be performed by study personnel at the study site. The urine sample collected for urinalysis will be sent to LabCorp for testing.

In case of any positive pregnancy test, the Investigator or designee will inform the participant about the risks associated with smoking during pregnancy.

In the event of a positive urine drug test for cocaine, THC, opiates, amphetamines, or methamphetamines at the screening visit (V1), participants are notified that they have been excluded from study participation because of a positive drug test.

Urinalysis
pH
Red blood cell traces
Bilirubin
Protein
Glucose
Specific gravity
Nitrite
WBC Esterase

Table 1 - Urinalysis Assessments

Drug Screening
Amphetamine
Cocaine
THC
Methamphetamine
Opiates

Table 2 - Drug Screening

### 8.2.3 Serum Pregnancy Test

Serum pregnancy test will be performed during the screening visit for all females.

Serum Pregnancy Test
Quantitative human chorionic gonadotropin (HCG) test

### 8.2.4 Urine Pregnancy Test

The urine pregnancy test will be performed by study personnel on site for all females at each visit (except screening).

### 8.2.5 Electrocardiogram (ECG)

ECG recording will be performed as per the site's standard operating procedures. A standard 12-lead ECG will be recorded after the participant has rested for at least 5 minutes in a supine position.

The following parameters will be documented: heart rate, PR interval, QRS interval, QT interval, and QTc interval. Every ECG will be assessed as normal, abnormal – not clinically significant, or abnormal – clinically significant.

ECG print-outs will be interpreted by a qualified physician or licensed medical provider. Any print-outs of ECGs on thermo-sensitive paper must be photocopied and stapled together for inclusion in the source documents and signed by the Investigator or designee.

### 8.2.6 Vital Signs

Vital signs (systolic and diastolic blood pressure, pulse rate, temperature and respiratory rate), will be measured in sitting position after the participant has rested for at least 5 minutes. After two minutes of standing, a second blood pressure reading (systolic and diastolic) and pulse rate will be obtained at the screening visit (V1).

### 8.2.7 Physical Examination

A complete physical examination, including auscultation and palpation will be performed. A complete physical examination will include review of general appearance, hair and skin, head, eyes, ears, nose and throat, neck, chest, abdomen, dentition, cardiovascular, musculoskeletal and neurological systems. The physical examination is to be conducted by a designated fully trained representative.

Appropriate medical recommendations will be provided to the participant if any medical findings requiring health care are identified.

### 8.2.8 Expired Air CO Breath Test

Carbon Monoxide (CO) in participant's exhaled breath (expressed as ppm) will be measured using a Vitalograph CO Monitor. Participants must have an expired air CO reading at V1 of at least 10 ppm for inclusion into this study. This test will be repeated at each of the sessions.

### 8.2.9 Medical History and Concomitant Disease

Relevant medical history and concomitant disease will be documented at the screening visit (V1). Medical history is defined as any condition that started and ended prior to screening. A concomitant disease is defined as any condition that started prior to screening and is still ongoing at V1 (this may also include findings detected during the screening visit (V1)).

### 8.2.10 Prior and Concomitant Medication

All medication taken 30 days prior to the screening visit (V1) and during the study will be documented. Medications which are stopped before the screening visit (V1) will be considered as prior medication. Medications which are started prior to the screening visit (V1) and which are still being taken by the participant during the study, as well as medications that are initiated after the screening visit (V1) will be considered as concomitant medications. This applies to both prescription and over-the-counter products (e.g., vitamins).

Records of prior and concomitant medications taken include the drug name (preferably both generic and trade name), route of administration, dose/unit, frequency of use, indication, the start and, if applicable, the stop date. Any therapy changes (including changes of regimen) during the study will be documented.

### 8.2.11 Body Height and Body Weight

Body weight will be measured at each visit. Height and weight will be measured at screening, and body mass index (BMI) will be calculated.

### 8.2.12 Demographics

Sex, date of birth, race and ethnicity will be recorded for each participant according to Section 8.5.

### 8.2.13 AE/SAE Reporting

AEs/SAEs will be assessed using questionnaires and interviews at the indicated time points and spontaneous reporting from the time of ICF signature until the EOS for the participant (see Section 8.5).

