## 3 INVESTIGATIONAL PLAN

### 3.1 OVERALL STUDY DESIGN AND PLAN

This single-group, small-scale, open-label study (N= 25 to 50) will evaluate the impact of combination zonisamide and bupropion on the process of switching from combustible cigarettes (CC) to an e-cigarette. There will be a data collection period of at least five days to obtain baseline data on use of combustible cigarettes. Participants enrolled in the study will receive a G6 e-cigarette at V2 for *ad libitum* use. After the first week of e-cigarette use, (at V3) participants will be given zonisamide (100 mg/daily) and will begin extended-release bupropion dosing (150 mg each morning days 1-3, then 300 mg/daily) in addition to continued use of the G6. At each visit, participants will receive enough zonisamide, bupropion, and Halo G6 cartomizers to last until their next study visit. Halo G6 and combination zonisamide and bupropion use will continue until the participant returns for the End-of-Study visit (V7).

[figure not shown]

Figure 1 - Overall Study Design

The outcome of the combination zonisamide and bupropion on the process of switching from combustible cigarettes (CC) to an e-cigarette will be compared to the following benchmarks. Initial results will fall into one of the following three categories:

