### **8.4 6-MONTH FOLLOW UP**

Participants who complete the study will be contacted six months after the switch day utilizing an automated SMS messaging system, to ascertain their current smoking status and use of e-cigarettes. If a participant self-reports current abstinence from smoking they will be asked to return to the office for collection of an expired air CO for verification.

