### 9.1.4 Tobacco Withdrawal

To the extent that nicotine or other tobacco smoke constituent intake is reduced or eliminated, participants may experience tobacco withdrawal symptoms, including craving, difficulty concentrating, mood disturbance and increased appetite/weight gain.

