### 11.1.2 Serious Adverse Event

A Serious Adverse Event is any adverse event that:

- results in death;
- is life-threatening;
- results in inpatient hospitalization or prolongation of existing hospitalization;
- results in persistent or significant disability / incapacity;
- results in a congenital anomaly / birth defect;
- requires immediate medical or surgical intervention.

Important medical events that may not result in death, be life threatening, or require hospitalization may be considered an SAE, when, based on appropriate medical judgment, the event may jeopardize the participant, or the participant may require medical or surgical intervention to prevent one of the outcomes listed in the above definitions.

The term "life-threatening" in the definition of "serious" refers to an event in which the participant was at risk of death at the time of the event; it does not refer to an event, which hypothetically might have caused death if it were more severe.

Any pre-planned hospitalizations that are known at the time of signing the ICF will not be recorded as an SAE; however, they will be recorded as AE only. Any AE that occurs during this pre-planned hospitalization will be considered according to the above definitions.

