### 11.7 REPORTING AND FOLLOW-UP OF PREGNANCIES

All participants who are determined to be pregnant after enrollment will be discontinued from the study. Advice on the risk of smoking and smoking cessation will be provided by the study doctor (or qualified staff) and participants will be referred to the respective health care facility/health care provider for further support.

The Investigator is responsible for informing the IRB of any pregnancy that occurs during the study according to local regulations.

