## 12.4 DATA HANDLING

Data of all participants enrolled including screening failures and AE/SAEs during the study (from the time of informed consent to the end of the study of the participant) will be captured in the source documents.

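### No collection of new adverse events is planned after the End of Study, the day the Halo and both drugs stop, and pregnancies are not followed to outcome

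*Combined protocol and SAP*

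**What the plan says.** **Collection window.** Section 8.2.13 provides for questionnaires, interviews and "spontaneous reporting from the time of ICF signature until the EOS for the participant". Section 12.4 gives the same limits for data capture: "from the time of informed consent to the end of the study of the participant". The first sentence of the definition in 11.1.1 ties an adverse event to participation, and 11.2.1 documents new abnormal findings if they are detected during the study.

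**End of exposure.** Section 3.1 states: "Halo G6 and combination zonisamide and bupropion use will continue until the participant returns for the End-of-Study visit (V7". The schedule in 8.5 collects Halo products at V7 and dispenses none. Sections 6.4.1 and 7.4.1 collect all study drug at the End of Study, which they identify as Visit 7 or early termination.

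**After EOS.** Sections 11.2.1 and 11.4 follow events that are ongoing at EOS, 11.4 follows serious events that continue past it, and 11.8 follows events that led to discontinuation. The one later planned contact point is at month 6 after the switch (8.4). Completers receive a text "to ascertain their current smoking status and use of e-cigarettes", and those who report abstinence are asked to come in for a CO reading, paid under 4.7. The questions in 8.6.3 cover cigarettes, e-cigarettes and other nicotine products.

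**Pregnancy.** Section 11.1.2 includes among the seriousness criteria an event that "results in a congenital anomaly / birth defect". Section 11.7 states: "All participants who are determined to be pregnant after enrollment will be discontinued from the study". It then provides for advice, referral and notice to the IRB.

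**The concern.** Stopping two centrally acting drugs and the supplied nicotine product on one day is a point at which new symptoms might appear, and it is the point at which the plan stops looking. Section 9.1.4 names the general risk: "To the extent that nicotine or other tobacco smoke constituent intake is reduced or eliminated, participants may experience tobacco withdrawal symptoms", mood disturbance among them. The PHQ-9, given at every visit, has its last administration at V7.

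Any safety summary from this study will therefore describe the on-study period, which for a participant who completes is the on-treatment period. The combination may go on to randomised trials of about 200 people (3.1.1). A table with no off-treatment events could then be taken as evidence that there were none, when the plan contained no step to find them.

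The pregnancy provisions have the same gap. An outcome that the protocol classes as serious would normally become known only after the participant has left the study, and no step is described for learning of it.

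**Working it through.** **1. The plan's own product-use period.** Inputs: one week of Halo alone from V2 to V3 (3.1) and a 12-week dosing period (6.2).
1 + 12 = 13 weeks = 91 days; with the four-day visit window, 91 + 4 = 95 days.
This reproduces the 13 weeks plus up to four days in 5.3 and the 91 to 95 days in Appendix 15. The Halo and both drugs therefore run to the same visit, V7.

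**2. Planned collection of new events after last exposure.** Collection ends at EOS (8.2.13, 12.4). For a completer EOS is V7, and last use is at V7 (3.1). Day 91 − day 91 = 0 days.

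**3. Where the switch falls.** The participant instructions for both drugs put the switch about 7 days after drug start: day 7 + 7 = day 14 from V2.
V7 is then 91 − 14 = 77 days, or 11 weeks, after the switch. Those 11 weeks lie inside the window, with the PHQ-9 at V1 to V7 (8.2.14.1) and the Shiffman-Jarvik scale at V2 to V7 (8.5).

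**4. Gap to the next planned contact.** Assumption: six months is 26 weeks, or 182 days, after the switch.
14 + 182 = day 196; 196 − 91 = 105 days = 15 weeks.
Moving V7 by four days either way gives 101 to 109 days, or 14.4 to 15.6 weeks. This exceeds the 13 weeks of product use.

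**5. Do other provisions fill the gap?**
- 11.2.1 and 11.4: events ongoing at EOS and serious events that continue. These do not cover new onset.
- 11.8: events that caused discontinuation. These do not cover new onset.
- 11.5 and 11.6: IRB and FDA reporting, with no end date. They govern what is done with an event the site knows of and do not provide for finding one.
- 8.4 and 8.6.3: planned contact, but no health item, and completers only.

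**6. Pregnancy.** Participation lasts about 14 to 16 weeks (3.4). Assumption: about nine months from conception to birth, 9 × 52/12 = 39 weeks. Even if conception came at the very start of a 16-week participation, birth would come 39 − 16 = 23 weeks after its planned end, and later still relative to EOS because discontinuation brings EOS forward.

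**The case against.** The case on the other side is substantial, and much of it stands.

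- **A reader might infer that late events cannot be reported.** The documents do not say so. The reporting duties in 11.5 and 11.6 have no cut-off, the second sentence of 11.1.1 is broader than the first, and participants are given an emergency number (9.2) and told to call about depression or suicidal thoughts (drug instructions). The limit is on planned collection.
- **A reader might infer that the withdrawal risk in 9.1.4 lies wholly outside the window.** It does not. That section speaks of any reduction in nicotine or smoke constituents, which includes leaving cigarettes at the switch, and step 3 shows this is observed for about 11 weeks.
- **A reader might assume that nicotine stops at V7.** Only the free supply stops. The stated goal is to move dependence to e-cigarettes (1.1), month 6 is meant to show persistence of switching (13.1.1), and 8.6.3 asks about continued e-cigarette use.
- **A reader might want an expected number of missed events.** The documents give no rate for post-treatment events, so any such figure would be invention.
- **A reader might say a birth defect could never be observed.** That goes too far: the pregnancy is notified to the IRB, and an outcome might reach the site informally. Few pregnancies are likely among 25 to 50 participants, given the contraception and testing rules in 4.1.3.
- **Advancement depends only on switching counts (3.1.1 to 3.1.3).** True; a longer safety window would not alter that decision.

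None of this supplies a planned step for finding new events after EOS or for learning a pregnancy's outcome.

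**Conclusion.** The point holds in a limited form. For a participant who uses the products to V7, planned collection of new-onset events after last exposure is zero days, followed by about 15 weeks (14.4 to 15.6) before a contact that does not ask about health. What is missed is new onset after V7 or early termination, in unknown number. For pregnancy, the protocol lists a serious outcome and describes no planned way to learn of it.

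This rests on three readings: month 6 taken as 26 weeks; the switch on the approximate day in the participant instructions; and EOS for a participant discontinued for pregnancy taken from the early-termination wording in 6.4.1 and 7.4.1, because 4.5 fixes an EOS date expressly only for loss to follow-up. Someone who stops the drugs early but stays in the study would have some observed off-drug time.

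The primary outcome and the stopping rule are unaffected. This is an inexpensive improvement to the safety data. Sections 8.2.13, 11.1.2, 11.2.1, 11.4, 11.7 and 12.4 need to be reconciled.

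**What to change.** 1. In 8.2.13 and 12.4, move the end of the AE/SAE window from EOS to the month-6 contact, and state that any new event a participant reports to the site after V7 or early termination is recorded as an adverse event. Align 11.1.1, 11.2.1 and 11.4 with this.
2. Add one item to the 8.6.3 text asking about any new health problem since the last visit, with existing medical staff contacting those who answer yes to record the event. Ask the same question at the month-6 CO visit for self-reported abstainers (8.4).
3. In 11.7, have existing staff record the pregnancy outcome by telephone, and state that the SAE window stays open for it.
4. Tabulate events with onset after V7 or early termination separately from earlier ones.

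The cost is protocol wording, IRB review of the amendment (14.1), one text item and occasional calls. If the consent form does not already cover contact after discontinuation, it needs a sentence on it. No new visit or staff is required, and dosing and clinical management are untouched.

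The limits should be stated in the report: recall over about 15 weeks is imperfect, and the text goes to completers only, so participants who stop early are covered only by what they report themselves.
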